7.2 Secondary Endpoints

As secondary endpoints we will assess modifiable behaviors and will include the following:

- Health care utilization over the study period
- Change in Autonomous Motivation over the study period
- Change in Autonomy Support over the study period

7.3 Control of Bias and Confounding

This is a single arm feasibility study. Our participants may differ in important ways from those who choose not to participate in the study, which will limit generalizability of our findings. We will mention this as a limitation in any study data dissemination. In addition, we will compare demographic and utilization characteristics of enrolled participants to available summary data on women delivering at the enrollment sites.

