4.4 Study Population

4.4.1 Inclusion Criteria

- 1) Females age 14 – 45.
- 2) History of preterm birth at < 34 weeks gestation OR history of preterm birth at 34 – 36 weeks gestation with risk factors for recurrent preterm birth including: low preventive care utilization, tobacco use, obesity, depression or anxiety, history of unmet contraceptive needs.
- 3) Intention to seek infant pediatric primary care at one of the two study sites (Karabots and Cobbs Creek).
- 4) Medicaid insurance.

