4.4.2 Exclusion Criteria

- 1) History of sterilization procedure.
- 2) Plan to move away from the area or transfer pediatric primary care within six months of enrollment.
- 3) Limited English proficiency

We are excluding younger women and women with Limited English proficiency from this pilot work because we expect that their health care navigation and education needs, patterns of health care utilization, and barriers to health will be distinct from those of older women and women with English proficiency, and would not be well represented in this small pilot study. Subjects that do not meet all of the enrollment criteria may not be enrolled. Any violations of these criteria must be reported in accordance with IRB Policies and Procedures.

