6.2 Measures of Treatment Feasibility and Acceptability (Primary Outcome)

The primary outcome of this study is to assess feasibility and acceptability of the Care Coordination After Preterm Birth intervention. We will assess feasibility and acceptability using the following measures.

- *Screening rate (feasibility)*: The study team will compare the number of potentially eligible participants to those who complete screening questionnaires. The number of potentially eligible participants will be considered the number of preterm births with Medicaid insurance in a given month.
- *Recruitment rate (feasibility)*: The study team will track the proportion of eligible women screened who enroll in the study.
- *Reasons for non-participation (acceptability)*: For women who decline screening or enrollment we will ask them, if they are willing, to provide reasons for non-participation and potential study modifications that might have encouraged them to participate. Responses will be tabulated and reviewed for potential themes.
- *Retention rate (feasibility)*: The study team will track the proportion of enrolled participants who complete the intervention and the study assessments.
- *Assessment process (feasibility)*: The study team will track the proportion of the baseline, 3-month, and 6-month assessments that are completed.

- *Intervention usability (feasibility)*: Study interventionists will keep records of barriers and facilitators of the intervention content and procedures.
- *Family engagement and adherence (feasibility)*: Study interventionists will keep track of the proportion of contacts initiated that are completed, contacts initiated by participants, and participant use of resources and strategies discussed during the intervention, based on participant feedback.
- *Intervention fidelity (feasibility)*
 - *Care coordination fidelity*: We will quantify interventionist completion of screening tools, as well as other tasks outlined in the care plan, including focused education, navigation, and addressing barriers to care, screening.

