9.6 Informed Consent/Accent and HIPAA Authorization

9.6.1 Waiver of HIPAA Authorization to Screen Medical Records

We are requesting a waiver of HIPAA authorization to screen health records for women following birth to identify potentially eligible participants. This will ensure that women who are contacted appear to be eligible based on chart review.

The use of health record data for eligibility screening involves no more than a minimal risk to the privacy of individuals. Identifiers for potentially eligible participants (name, room number, telephone number) will be stored in a secure REDCap database and will be destroyed within two weeks for any potentially eligible participant who has not been contacted or who has been contacted by declined enrollment. As noted above, screening summary data will be retained (number potentially eligible, number completed screening, number consented to study participation) but these data will not include any protected health information. Individual screening data will not be used for study purposes (beyond screening). Screening data will not be reused or disclosed for any reason.

The research could not practicably be conducted without the waivers. Due to the large number of women delivering at HUP and the frequency of rapid discharges, a requirement to obtain HIPAA authorization for screening could introduce bias into recruitment with women with longer length of stay more likely to be identified as potentially eligible. In addition, the research could not be conducted without access to this data as there would be no practicable way to identify potentially eligible women.

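### The selection check in section 7.3 does not limit its comparator to eligible women, so it cannot separate eligibility effects from participation effects

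*Combined protocol and SAP*

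**What the plan says.** Section 7.3 (Control of Bias and Confounding) describes a single-arm feasibility study and states the worry directly: "Our participants may differ in important ways from those who choose not to participate in the study". It promises to report this as a limitation. It then adds one comparison of characteristics: "we will compare demographic and utilization characteristics of enrolled participants to available summary data on women delivering at the enrollment sites". No restriction by insurance, gestational age or any other entry criterion is given.

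The entry criteria are narrow. Section 4.4.1 requires "Medicaid insurance", intended pediatric care at one of two primary care sites, and "History of preterm birth at < 34 weeks gestation OR history of preterm birth at 34 – 36 weeks gestation with risk factors". The listed risk factors are "low preventive care utilization, tobacco use, obesity, depression or anxiety, history of unmet contraceptive needs". Section 4.4.2 excludes women with "Limited English proficiency", prior sterilization, or plans to move or transfer pediatric care.

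Two other sections bear on the point. For the screening rate, section 6.2 says that the number of potentially eligible women "will be considered the number of preterm births with Medicaid insurance in a given month". Section 9.6.1 says that "screening summary data will be retained (number potentially eligible, number completed screening, number consented to study participation", and it rules out using individual screening records for any study purpose other than screening.

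**The concern.** The bias named and the comparison planned concern different groups. Women who choose not to take part are eligible women who were invited, or could have been. Women delivering at the hospital include many who could never have been invited.

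This matters because the entry criteria act on the variables to be compared. Utilization is one of the two domains in section 7.3, and low preventive care use is one of the routes into the study at 34 to 36 weeks. Demographic profile will also shift with the Medicaid requirement and the choice of pediatric site. A gap could therefore be read as participation bias when eligibility produced it, or a small gap could be taken as reassurance when two opposing differences have cancelled.

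What is at stake is how far the feasibility findings can be generalized. Recruitment rate is itself one of the feasibility measures in sections 6.2 and 7.4.1, so it matters which eligible women were left out.

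**Working it through.** **Inputs from the protocol.** About 100 eligible women deliver each year, and the plan is to enroll 106 over two years (section 9.5). Preterm births are 10% of US births (section 2.1); the hospital's own share is not given.

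**Inputs assumed.** Section 7.3 gives no prevalences. For illustration, take a trait present in 40% of eligible women and in 10% to 40% of all women delivering, with a true difference (enrolled minus eligible non-participants) of -20, 0 or +20 points.

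**Step 1: room for participation bias.** Eligible women over two years: 100 × 2 = 200. Uptake u = 106/200 = 0.53. Not enrolled: 200 − 106 = 94, or 47%. The target of 106 fits within the pool, as section 9.5 says, but nearly half the pool is left outside the study.

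**Step 2: what the planned gap contains.** Write E for the trait's prevalence in enrolled women, N in eligible non-participants, P in all eligible women and C in the comparator.

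- P = u·E + (1 − u)·N, so E − P = (1 − u)(E − N).
- E − C = (P − C) + (1 − u)(E − N) = (P − C) + 0.47 × (E − N).

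The first term is the eligibility effect and the second is the participation effect. The check observes only their sum.

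**Step 3: numbers.** With P = 40%, a true difference of -20 points gives E = 40 − 0.47 × 20 = 30.6%. A difference of +20 points gives E = 49.4%.

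| Prevalence among all deliveries (assumed) | Gap seen, E − N = 0 | Gap seen, E − N = -20 | Gap seen, E − N = +20 |
|---|---|---|---|
| 10% | 30.0 | 20.6 | 39.4 |
| 20% | 20.0 | 10.6 | 29.4 |
| 30% | 10.0 | 0.6 | 19.4 |
| 40% | 0.0 | -9.4 | 9.4 |

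In the 30% row the check shows 10 points when participation is unbiased, and almost nothing when participants are 20 points below non-participants. Only in the last row, where eligible women resemble all women delivering, does the gap reflect participation alone.

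**Step 4: the same check against the eligible pool.** With C = P the first term is zero and the gap is 0.47 × (E − N). True differences of 10, 20 and 30 points would appear as 4.7, 9.4 and 14.1 points. They are diluted because the pool includes the participants, but they are in the right direction and can be interpreted.

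**Step 5: what else is planned.** Non-enrolled women are described by voluntary reasons for declining (section 6.2) and by three counts (section 9.6.1). Neither gives their characteristics, so nothing else in the plan supplies the missing comparison.

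**The case against.** The strongest reply is that section 7.3 leaves its comparator open and has not chosen a wrong one. It refers to whatever summary data are available on women delivering; it does not say all women. The team could obtain a Medicaid or preterm extract and still be following the plan. That stands, and it makes the defect one of specification. A reader might infer that the plan commits to comparing participants with every woman who delivers, but the text does not go that far.

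A reader might also infer that the comparison would reflect only the entry criteria and reveal nothing about participation. The algebra does not support that: the participation term is in the gap, weighted by 0.47. It is confounded with eligibility, not absent.

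The plan also has direct measures of non-participation: screening rate, recruitment rate and reasons for declining. These are useful, but they do not show whether decliners differ in demographics or prior care.

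The suggested comparator is imperfect too. Section 6.2 defines a monthly count of Medicaid preterm births, not a profile, and a profile may be harder to obtain. The group would still differ from participants through the remaining entry criteria. Both points are fair, and the fix should state them.

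Finally, this is a descriptive single-arm pilot with no power calculation, and section 7.3 already commits to disclosing the limitation. That bears on priority and is accepted.

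**Conclusion.** The concern holds in a limited form. As written, the comparator in section 7.3 is not confined to eligible women, so differences due to eligibility cannot be separated from differences due to participation. The check can show a gap without participation bias and can hide one that exists.

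The size rests on two things. The 47% non-enrolled comes from the protocol's own approximate figures and assumes that the full 106 are enrolled from the 200. Section 9.5 also allows women to be identified through the primary care sites, and recruitment may stop early, so the true share could differ. The 10-point and 0.6-point gaps rest on assumed prevalences and illustrate the mechanism; they do not predict a result. The US figure implies that about 90% of women delivering had term births (1 − 0.10). That shows how broad an unrestricted comparator could be, but it is not a difference in any characteristic to be compared.

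It may be tempting to conclude that tabulating the characteristics of decliners would cost almost nothing because screening summaries are already kept. Section 9.6.1 does not support this: it lists three counts and bars other study use of individual screening records.

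Priority is low. No endpoint, test or sample size depends on the comparison.

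**What to change.** In section 7.3:

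- Define the comparator as aggregate data on Medicaid-insured preterm deliveries at the delivery hospital during the enrollment period, which is the denominator section 6.2 already uses. Split it at 34 weeks where the data allow. Name the hospital, since the two primary care sites are not places of delivery.
- Compare utilization before enrollment, such as the number of prenatal visits and the timing of the first one, which section 5.2 already collects for participants. Later utilization is a study outcome that the intervention is meant to change.
- State that differences due to the other criteria will remain: risk factors at 34 to 36 weeks, choice of pediatric site, language, sterilization and planned moves.

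The cost is a few sentences of protocol text and a narrower aggregate extract, which may be less readily available than overall delivery data. No individual screening records are needed.

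An optional further step is to keep aggregate tallies of eligible women who did not enroll, by bands of age, gestational age and prenatal visits. That would come closest to the question section 7.3 asks, but it requires amending section 9.6.1 and is not part of the low-cost change.

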7.4 Statistical Methods

7.4.1 Primary outcome: Feasibility data

We will examine the following quantitative feasibility and acceptability outcomes through the use of descriptive statistics, which include means for continuous variables and proportions for categorical variables. In some cases, we will compare them to a priori goals for feasibility. See above (Section 5) for more detail about measurement of these outcomes.

- Screening rate: Proportion of potentially eligible participants screened.
- Recruitment rate: Proportion of screened women who enroll.
- Retention rate: Proportion of enrolled participants who complete the intervention and the study assessments.
- Assessment process: Proportion of the baseline, 3-month, and 6-month assessments that are completed.
- Family engagement and adherence: Proportion of contacts initiated that are completed within 3 days will be compared to an a priori threshold of 80%, # of contacts initiated by participants, # of recommended resources utilized.
- Intervention fidelity
 - Care coordination fidelity: # of screenings completed, # of care plan goals achieved
 - Motivational interviewing fidelity: OnePass score will be compared to an a priori threshold of 5, considered a minimum threshold for competence.

7.4.2 Quantitative secondary outcomes

We will also examine the following quantitative secondary outcomes through the use of descriptive statistics, which include means for continuous variables and proportions for categorical variables.

- Count of preventive care visits
- Proportion of preventive care recommended in care plan that is completed
- Change in autonomy support
- Change in autonomous motivation

7.4.3 Qualitative data

Qualitative data (itemized below) will be reviewed and assessed for themes using a priori codes related to theories of acceptability and feasibility,⁷⁰ as well as a grounded theory approach where we allow themes to emerge from data. (For more details on how these data will be defined and collected, see Section 5 above.)

- Reasons for non-participation
- Intervention usability
- Family engagement and adherence (participant feedback)
- Intervention acceptability

7.4.4 Safety Analysis

This is a minimal risk study and therefore we do not anticipate any adverse events related to study participation. However, for all subjects who consent to participation we will track and describe any adverse events that occur during the study.

7.5 Sample Size and Power

This open single arm study is not designed to have power to test the efficacy or significance of the intervention effects. A power analysis was thus not appropriate. The sample size for this study was identified through review of the literature on testing preliminary interventions.

8 SAFETY MANAGEMENT

8.1 Clinical Adverse Events

Clinical adverse events (AEs) will be monitored throughout the study.

8.2 Adverse Event Reporting

Since the study procedures are not greater than minimal risk, SAEs are not expected. If any unanticipated problems related to the research involving risks to subjects or others happen during the course of this study (including SAEs) they will be reported to the IRB in accordance with CHOP IRB SOP 408: Unanticipated Problems Involving Risks to Subjects. AEs that are not serious but that are notable and could involve risks to subjects will be summarized in narrative or other format and submitted to the IRB at the time of continuing review.

9 STUDY ADMINISTRATION

9.1 Treatment Assignment Methods

There will be no randomization and no blinding in this study.

9.2 Data Collection and Management

Here we describe a data collection and management plan that is consistent with CHOP Policy A-3-6: Acceptable Use of Technology Resources that defines the requirements for encryption and security of computer systems

Confidentiality: All study data (with the exception of qualitative audio recordings, see below) will be maintained on in a password-protected RedCap database that will only be available to members of the study team. This database will contain Protected Health Information. At the conclusion of data collection (i.e. after completing the 6-month study assessment), study staff will convert each record to a “Coded” record through two steps. First, we will create creating a separate RedCap database (the Master List) that includes only the study identification number, subject name, and subject date of birth. Second, we will remove all PHI from the main study database but removing identifying information and converting dates into times from most recent birth. Data entry into RedCap will involve a combination of direct participant entry, study team entry from participant report, and study team entry from health record review. Only coded data will be downloaded from RedCap for analysis. When coded data is downloaded, it will be stored in password protected folders on the CHOP network drives.

All paper consent forms will be stored in a locked filing cabinet in the Roberts Center for Pediatric Research. They will also be scanned and stored in password protected files on the CHOP network drive.

Qualitative data will be collected via audio-recording in-person or over the phone or video. All audio files will be stored on the secure CHOP computer network drive in password protected folders accessible only to members of the study team. Transfer of audio files from the audio device to the CHOP network drive will via cable directly from the device to the computer or via an encrypted flash drive. In the password protected file, audio

files will be labeled with only the participants' study ID. Audio files will be transcribed by a professional transcription agency that functions in accordance with all CHOP technology transfer policies. We will contact OTT to ensure that a Business Associate Agreement is in place for the transcription agency. Transcripts will be stored in password protected files on the CHOP network drives and will be de-identified by removing any references to names, dates, or specific addresses. Audio files will be maintained until analysis is complete, to assist with any uncertainties in the analysis of the data.

Security: The CHOP REDCap system operates with back-up recovery systems in place. Consent forms will have a paper back-up system available. Qualitative transcripts will have a back-up stored locally on the CHOP-issued computer of the study PI in a password protected folder.

Anonymization, de-identification, or destruction of data: Plans to de-identify and code data are described above (see “Confidentiality”). All study data will be retained a minimum of 6 years from study start completion, consistent with current CHOP policies on retention and destruction of records for Human Subjects Research with minimal risk. Data files will include instructions about study start date to assist the study team with completing destruction of data.

9.3 Confidentiality

All data and records generated during this study will be kept confidential in accordance with Institutional policies and HIPAA on subject privacy. The PI and all members of the study team will not use data and records for any purpose other than conducting the study. All members of the study team will complete training on confidentiality in research. All data will be safeguarded as described above.

No identifiable data will be used for future study without first obtaining IRB approval. The investigator will obtain a data use agreement between the provider (the PI) of the data and any recipient researchers (including others at CHOP) before sharing a limited dataset (PHI limited to dates and zip codes).

9.4 Regulatory and Ethical Considerations

9.4.1 Data and Safety Monitoring Plan

In this minimal risk study, the primary anticipated safety risk relates to disclosure of sensitive information to study team members. This information includes information on mental health symptoms which are explicitly included in study data collection (Edinburgh Postnatal Depression Scale). In addition, though we are not explicitly asking participants to report on or discuss instances of abuse and neglect for either themselves or their infants, these issues may be disclosed. Finally, study team members may directly observe signs of abuse or neglect or signs of mental health deterioration.

We will ensure that all study team members have completed training for identifying abuse and neglect as well as severe mental health symptoms, and are also trained in reporting requirements. In addition, we have developed the following protocol to address any instances of safety concerns.

- **Mild to moderate behavioral health concerns that are not currently being treated:** Research staff will offer a resource sheet (included in IRB application as attachment) for community resources. This intervention will be embedded in two CHOP primary care sites. Therefore, study staff may also remind participants that social workers associated with their child's care site are available to help parents navigate access to behavioral health services for themselves.
- **Severe behavioral health concerns that are not currently being treated:** This includes any mention of current thoughts or acts of self-harm or harm to others. In these situations, staff will notify the Principal Investigator (a licensed pediatrician) who will speak to the participant immediately, if time permits, or by phone as soon as possible. If indicated, suicidality will be assessed using the suicidal thoughts item from the Edinburgh Postnatal Depression Scale, which is currently the standard scale to assess maternal mental health in the Care Network. Item 10 of this scale reads "Over the last two weeks, the thought of harming myself has occurred to me..." response options include "yes, quite often," "sometimes," "hardly ever," and "never." Should there be an imminent risk to caregiver safety, study staff or the Principal Investigator will contact emergency services (911 or Pennsylvania mobile crisis services) for further suicide/homicide/risk assessment. If for some reason the Principal Investigator is not available in an emergency situation, study team members will contact the social work team associated with the child's care site for guidance.
- **Child abuse or neglect:** Should a caregiver spontaneously disclose incidents of abuse or neglect, we will file a report with Department of Human Services.
- **Intimate partner violence:** If a caregiver spontaneously discloses incidents of intimate partner violence, they will be offered a resource sheet (included in the IRB application as an attachment) about IPV resources. If they report ongoing intimate partner violence, they will be connected with the IPV specialist affiliated with the study sites to conduct further assessment and develop a safety plan. If there is concern for an immediate safety issue, study team members will immediately notify the principal investigator or, if she is not available for some reason, the IPV specialist associated with the child's care site.

Any referrals or follow-up activities related to the above safety concerns will ***not*** be documented in patient health records by the study team. In situations where an immediate safety concern was noted in study materials (recordings / transcripts), the transcript will be annotated to indicate any immediate or follow-up actions taken to address those concerns.

Resource sheets were adapted from sheets used for a parenting intervention currently underway in the Care Network with oversite from the CHOP IRB. In addition, this protocol has been in place for CHOP IRB exempt qualitative work preliminary to the current study.

This study is covered by a **Certificate of Confidentiality** to protect identifiable information from forced disclosure. The CoC will allow all individuals who have access to research records to refuse to disclose identifying information on research participants in any civil, criminal, administrative, legislative, or other proceeding, whether at the federal, state, or local level. By protecting researchers and institutions from being compelled to disclose information that would identify research subjects, the CoC will help achieve the research objectives and promote participation in the study by ensuring confidentiality and privacy.

The PI for this study to review data storage and integrity, safety events, and other adverse events at least once every six month. These will be reported during continuing reviews to the IRB and the study sponsor. Any unanticipated severe events or episodes of reported abuse or neglect will be urgently reviewed by the PI to ensure reporting to the CHOP IRB and the study sponsor and the review protocols to assess for any needed revisions to ensure participant safety.

